9 DOSE LIMITING TOXICITY

9.1 Definition of a Dose Limiting Toxicity

All patients who have received at least one dose of atovaquone will be evaluable for DLTs.

DLTs are defined as any of the following occurring between the start of trial treatment until three months post CRT, and assessed by the Principal Investigator as possibly, probably or definitely related to atovaquone and/or to chemoradiotherapy. If an event is believed to be possibly, probably or definitely related to treatment with Durvalumab rather than trial IMPs, it may be reported as an SAE rather than a DLT.

DLTs will be defined as per NCI CTCAE v4.03 and include:

- Grade \geq 4 absolute neutrophil count (ANC) (<0.5 x 10⁹/L) for >7 days
- Grade ≥3 febrile neutropenia (fever of unknown origin without clinically or microbiologically documented infection) (ANC <1.0 x 10⁹/L, fever ≥38.5°C) lasting >3 days
- Infection (documented clinically or microbiologically) with grade 3 or 4 neutropenia (ANC <1.0 x 10⁹/L)
- Grade \geq 3 thrombocytopenia (platelets <25 x 10⁹/L)
- Clinically significant bleeding attributed to grade 3 thrombocytopenia or requiring platelet transfusion
- Grade ≥3 oesophagitis
- Grade ≥3 pneumonitis onset within 3 months of starting radiotherapy
- Grade ≥3 nausea or vomiting not controlled by optimal outpatient anti-emetic treatment for ≥5 days
- Grade ≥3 diarrhoea despite optimal outpatient anti-diarrhoeal medication use
- Any toxicity causing a delay of radiotherapy completion by greater than one week
- An elevation of ALT or AST >5 x ULN lasting 8 days or more
- A concurrent elevation of ALT or AST (>3 × ULN) and total bilirubin (>2 × ULN) in whom there is no evidence of biliary obstruction or other causes that can reasonably explain the concurrent elevation
- Other grade ≥3 effects thought to be clinically significant and directly related to the combination of atovaquone with chemoradiotherapy

Dose limiting toxicities must be reported within 24 hours of the site becoming aware using the SAE form (even if the event does not meet the definition of an SAE). Scan the form and email as an attachment to [contact].

See section 14 for safety reporting procedures.

DLTs will be processed to support dose decisions according to procedures detailed in Section 17 and the separate Protocol Decision Point Plan.

10 **OTHER TREATMENTS (NON-IMPS)**

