14.2 Clinical laboratory abnormalities and other abnormal assessments as AEs and SAEs

Abnormal laboratory findings (e.g. clinical chemistry, haematology, urinalysis) or other abnormal assessments (e.g. electrocardiograms, X-rays and scans) that are judged by the Investigator as clinically significant will be recorded as AEs or SAEs if they meet the definitions given above. **By definition, all CTCAE Grade 3 or 4 laboratory abnormalities should usually be reported as SAEs.** However, if a lab result is categorised as Grade 3 or 4 but did not fulfil the safety reporting criteria for an SAE (asymptomatic, not life threatening, no intervention), it is the clinician's decision whether to report the event. If the event is not reported the reason why should be documented in the patient notes.

If a laboratory abnormality is part of a diagnosis, the diagnosis should be reported as an AE/SAE. If possible, the laboratory abnormality should be recorded as a medical term and not simply as an abnormal laboratory result (e.g. record thrombocytopenia rather than decreased platelets). Discuss with clinician regarding significance.

Clinically significant abnormal laboratory findings or other abnormal assessments that are detected during the study or are present at baseline and significantly worsen following the start of the study will be reported as AEs or SAEs. However, clinically significant abnormal laboratory findings or other abnormal assessments that are associated with the disease being studied, unless judged by the Investigator as more severe than expected for the patient's condition, or that are present or detected at the start of the study and do not worsen, will not be reported as AEs or SAEs.

The Investigator will exercise his or her medical and scientific judgment in deciding whether an abnormal laboratory finding or other abnormal assessment is clinically significant.

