14.8 Reporting Adverse Events on the CRF

All AEs, including Serious AEs must be recorded on the eCRF for registered patients, unless otherwise specified in section 14.9. The information provided will include date of onset, event diagnosis (if known) or sign/symptom, severity, time course, duration and outcome and relationship of the AE to study drug. Any concomitant medications or any other therapy used to treat the event must be listed. The Investigator will provide an "other" cause for serious AEs considered to be unrelated to the study drug. Sites should ensure data entered into the eCRF is consistent with the SAE report information where applicable.

Each separate AE episode must be recorded. For example, if an AE resolves completely or resolves to baseline and then recurs or worsens again, this must be recorded as a separate AE. For AEs to be considered intermittent, the events must be of similar nature and severity.

AEs may be spontaneously reported by the patient and/or in response to an open question from study personnel or revealed by observation, physical examination, or other diagnostic procedures. Any clinically relevant deterioration in laboratory assessments or other clinical finding is considered an AE.

Terms and Grading of Events

All adverse events and toxicities must be graded according to the NCI Common Terminology Criteria for adverse events (NCI CTCAE) Version 4.0 (currently up to Version 4.03). Toxicity grades should be recorded on the eCRF. These will be coded by OCTO to the MedDRA version current on the date of MHRA approval of the trial.

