All other grade <2 AEs, assessments, abnormal laboratory results, if clinically				
significant			х	
Grade ≥3 laboratory results not fulfilling safety reporting criteria		X1	X1	
Disease progression and death	Email repo	rting form	Report in	Non-
Disease progression and death	within 2	4 hours	AE CRF	reportable
Clinical symptoms, assessments or laboratory results associated with disease progression				x
Hospitalisation for disease progression				х
Non-emergency admission for feeding tube placement				X
A visit to accident and emergency or other hospital department for less than 24				~
hours, that does not result in admission (unless considered an important				х
medical or life-threatening event)				~
Admissions as per protocol for a planned medical/surgical procedure				х
Routine health assessment requiring admission for baseline/trending of health	1	1		
status				х
Medical/surgical admission other than to remedy ill health and planned prior to	1	1		
entry into the study				х
Admission encountered for another life circumstance that carries no bearing on				
health status and requires no medical/surgical intervention				x
Admission for administration of anti-cancer therapy in the absence of any other				
SAEs				х
Death	1	X ²	X ³	

¹ If a lab result is categorised as Grade 3 or 4 but did not fulfil the safety reporting criteria for an SAE (asymptomatic, not life threatening, no intervention), it is the clinician's decision whether to report the event. If the event is not reported the reason why should be documented in the patient notes.

² If death is possibly related directly to atovaquone or the combination of atovaquone + radiotherapy +/- chemotherapy.

³ Providing the death is not unexpected or if a causal relationship is not suspected. The investigator must clearly state whether a causal relationship to atovaquone + radiotherapy +/- chemotherapy is suspected, and if so, whether the death was expected or unexpected.

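### Protocol 14.2 and footnote 1 of 14.11 make AE CRF entry of some grade 3 or higher laboratory results optional although 14.8 requires it, so the graded safety table can be under-counted

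*Protocol*

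**What the plan says.** Protocol 14.2 sets a default that "all CTCAE Grade 3 or 4 laboratory abnormalities should usually be reported as SAEs". It then makes an exception for a grade 3 or 4 result that does not meet the SAE criteria, described as one without symptoms, without threat to life and without any intervention. For such a result, "it is the clinician's decision whether to report the event", and "If the event is not reported the reason why should be documented in the patient notes".

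The summary table in 14.11 repeats the exception in the row "Grade ≥3 laboratory results not fulfilling safety reporting criteria". That row carries the footnoted mark in two columns. By alignment with the neighbouring rows, these are the 24-hour form and the AE CRF. A separate row for other clinically significant events of grade 3 or above, laboratory results included, marks the same two columns without a footnote.

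Protocol 14.8 sets the recording rule: "All AEs, including Serious AEs must be recorded on the eCRF for registered patients, unless otherwise specified in section 14.9". It adds that "Any clinically relevant deterioration in laboratory assessments or other clinical finding is considered an AE". The exemptions in 14.9 cover disease progression, death from the disease, and elective or supportive admissions. Laboratory results are not among them.

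The first secondary endpoint is adverse events by CTCAE grade. Protocol 18.1 tabulates toxicity by type and grade, and SAP 6.1 presents adverse events from first dose to six months after CRT.

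**The concern.** An exception that looks designed to spare sites needless expedited reports also releases them from the CRF entry. The safety table is built from adverse events on the CRF, so a result left off the CRF is absent from the table, and the only trace of the decision is in the hospital notes. Two clinicians following the protocol faithfully could record the same laboratory value differently. With 20 patients at two centres, spread over up to four dose levels, each count in the table is small, and a few omissions could change how the haematological and liver profile reads.

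**Working it through.** The documents state no figure to reproduce, so the check is a comparison of rules, followed by an illustration of size.

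**1. What opens the exception.** Under 14.2 and footnote 1 of 14.11, it is failure to meet the SAE criteria. Clinical significance is not mentioned in either place.

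**2. What makes a laboratory result an AE.** Under 14.1 it must be significant, and under 14.8 clinically relevant. Other sentences in 14.2 say that clinically significant findings are to be recorded or reported as AEs or SAEs. Seriousness plays no part in this test.

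**3. The two tests crossed, for a result of grade 3 or above:**

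| Type of result | 14.2 exception and footnote 1 | 14.8 and the unfootnoted row of 14.11 | Consistent? |
|---|---|---|---|
| Meets SAE criteria | Does not apply | Must be recorded | Yes |
| Not serious, not clinically significant | Optional | Not an AE, so not required | Yes |
| Not serious, clinically significant | Optional | Must be recorded | No |
| Meets a DLT criterion | Not mentioned | Mandatory under 9.1, 14.1 and the DLT rows of 14.11 | Yes, though the precedence is not stated in 14.2 |

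The conflict is confined to the third row.

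**4. Whether an omission would be noticed.** Protocol 20.2 has appropriate laboratory data transcribed to the CRF, but no rule in either document derives a CTCAE grade from those values. Protocol 17.3 limits source data verification to what the risk assessment indicates. SAP 5.6 describes checks for completeness and for consistency across CRFs, without a check of laboratory values against AE entries. SAP 6.3 plans no imputation. SAP Appendix 3, which holds the table templates, is a separate document and was not available. If it contains laboratory tables by grade, part of the loss would be recoverable.

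**5. Size.** Let N be the number of evaluable patients (20; protocol 17.4), p the share of patients with a clinically relevant but non-serious laboratory result of grade 3 or above, and f the fraction of those left off the CRF. Patients missing from the table = N × p × f. Neither p nor f is given, so both are assumed: p from 0.10 to 0.30 (2 to 6 patients) and f from 0.25 to 1.00.

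- Low end: 20 × 0.10 × 0.25 = 0.5 patients.
- High end: 20 × 0.30 × 1.00 = 6 patients.
- If every clinician chooses to record (f = 0), nothing is lost.

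The rates in protocol 12.5 (neutrophils 15%, white cells 13%, lymphocytes 11%) cannot stand in for p. The table does not state their grade, and it does not separate results that were silent and untreated.

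**The case against.** The strongest reply is that the clauses should be read together. A result that is not clinically significant is not an AE, a significant one has its own mandatory row, and so the optional row covers only the insignificant remainder. That is probably what was intended, and it removes any conflict for insignificant results. It does not settle the third row of the comparison, because neither 14.2 nor footnote 1 limits the choice to insignificant results. A clinically significant, non-serious result fits both table rows, and nothing says which governs.

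The exception is also narrow: all three conditions must hold, including that there was no intervention. The guide in 8.6 attaches a dose delay, omission or reduction, or added supportive treatment, to many low counts and raised liver tests, so many such results may fall outside it. This stands as a limit on size. But the guide is advisory and tied to chemotherapy dosing, and the protocol does not say whether a delayed dose counts as an intervention.

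Third, the table is descriptive. SAP 6.2 plans no formal analysis of secondary objectives, and neither document plans a comparison with the rates in 12.5. This also stands: no test or planned comparison is biased, only the reported profile.

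A reader might go further and infer that a dose limiting toxicity resting on laboratory values alone could go unreported, since four of the 13 criteria in 9.1 are of that kind. The documents do not support this. Section 9.1 states: "Dose limiting toxicities must be reported within 24 hours of the site becoming aware using the SAE form", whether or not the event is otherwise an SAE. Section 14.1 says twice that such events go through SAE reporting, and the corresponding rows of 14.11 carry no footnote. The visit schedule includes DLT assessment, and SAP 6.3 describes a dedicated CRF for dose decisions. What is left is a missing cross-reference.

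**Conclusion.** The point holds for the secondary safety endpoint only. The protocol gives two incompatible instructions for a laboratory result of grade 3 or above that is clinically relevant but not serious, and one of them allows it to be left off the AE CRF with the reason held only in the patient notes. The graded toxicity table can therefore be too low, and can vary with the clinician or site. The size is unknown: 0.5 to 6 of 20 patients follows from assumed inputs and is not an estimate, and the loss could be nil. The conclusion rests on reading the two footnoted marks in 14.11 as the 24-hour form and the AE CRF, which the neighbouring rows support. Neither the MTD nor the stopping rule is touched. The change is worth making because it is cheap and removes an avoidable source of inconsistency; the trial's main conclusion does not depend on it.

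**What to change.** In 14.2 and footnote 1 of 14.11, state that the clinician's choice concerns the expedited SAE form only, and take the footnote off the AE CRF column. Then secure the record in one of two ways:

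- require every laboratory result of grade 3 or above on the AE CRF, with a flag for clinical significance so that insignificant values can be tabulated separately; or
- derive the CTCAE grade centrally from the laboratory values transcribed to the CRF, and say so in the SAP.

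The overlapping row for clinically significant events also marks the 24-hour form, so the amended text should say which row governs that form for a significant but non-serious result.

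Two clarifications can go into the same amendment. First, add that the choice never applies to an event meeting a criterion in 9.1. Second, correct the row beginning "All other grade <2 AEs, assessments, abnormal laboratory results, if clinically" so that it includes grade 2. As printed, grade 2 has no row, although 14.8 already requires all AEs to be recorded.

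The cost is a wording amendment and a few more CRF entries per patient, some of them for values of no clinical significance. No extra blood tests are needed.

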14.3 Determining adverse event causality

A Serious Adverse Reaction (SAR) is a SAE that may be related to any IMP either on its own or in combination with RT. The assessment of "relatedness" must be determined by a medically qualified individual and is primarily the responsibility of the PI at site or agreed designee. AEs that will be considered related will include any AE that is documented as possibly, probably or definitely related to protocol treatment. The assessment of relatedness is made using the following:

Classification	Relationship	Definition		
Drug-related Pro	Definitely related	 Starts within a time related to the study drug administration and No obvious alternative medical explanation 		
	Probably related	 Starts within a time related to the study drug administration an Cannot be reasonably explained by known characteristics of th patient's clinical state 		
	Possibly related	 Starts within a time related to the study drug administration and A causal relationship between the study drug and the adverse event is at least a reasonable possibility 		
Not drug related	Probably not related	• The time association or the patient's clinical state is such that the study drug is not likely to have had an association with the observed effect.		
	Definitely not related	 The AE is definitely not associated with the study drug administered 		

The Investigator must endeavour to obtain sufficient information to confirm the causality of the adverse event (i.e. relation to surgery, study drug, background treatment, other illness, progressive malignancy etc.) and give their opinion of the causal relationship between each AE and study drug. This may require instituting supplementary investigations of significant AEs based on their clinical judgement of the likely causative factors and/or include seeking a further specialist opinion.

14.4 Reference safety information (RSI) for assessment of expectedness

The reference safety information (RSI) for the trial which lists all the expected side effects associated with trial treatment is:

- For atovaquone: section 4.8 of the SmPC for atovaquone.
- **For cisplatin:** section 4.8 of the SmPC for cisplatin.
- **For vinorelbine:** section 4.8 of the SmPC for vinorelbine.

Please note that the list of expected side effects in the atovaquone SmPC are those listed for treatment of mild to moderate Pneumocystis pneumonia and in patients who are intolerant of co-trimoxazole therapy. It is therefore possible that in this study population other side effects may occur, or the patient might suffer a more severe reaction.

Equally, the list of expected side effects in the SmPCs for cisplatin and vinorelbine are those listed for patients receiving standard chemoradiotherapy or chemotherapy alone. It is therefore possible that in this study population, where combination of atovaquone is used with standard chemoradiotherapy, other side effects may occur, or the patient might suffer a more severe reaction.

A copy of the current approved version of the RSI documents must be held in the Investigator Site File for reference. The SmPCs used as RSI are the versions provided by OCTO (approved for use in this trial by the MHRA). It is not specified that any particular brand of cisplatin or vinorelbine must be prescribed, however irrespective of the brand prescribed, the RSI to be referenced is provided by OCTO. N.B. this may not be the latest SmPC version available online. Any change or update to the RSI during the trial will be made via a substantial amendment.

Expected AEs due to chemoradiotherapy are listed in section 12.5.

14.5 Suspected Unexpected Serious Adverse Drug Reactions (SUSARs)

All SUSARS will be reported to the Responsible Authority and main REC by the Trial Office within the required timelines:

- Fatal or life threatening SUSARs will be reported within seven days of the Trial Office receiving the initial report. Any additional significant information will be reported within eight days of sending the first report.
- All other SUSARs will be reported within 15 days of the Trial Office receiving the initial report. Any additional, significant information must be reported within a further 15 days.

In addition, other safety issues qualify for expedited reporting where they might materially alter the current risk assessment of an IMP or be sufficient to change IMP administration or the overall conduct of the trial.

14.6 Expedited reporting of SAEs

The following SAE reporting requirements apply regardless of the Investigator's assessment of the causality or expectedness of the SAE. All SAEs should be notified to the Trial Manager by phone or email and reported on the trial SAE report form (see SAE report form and completion guidelines). This should be completed, scanned and emailed within 24 hours of becoming aware of the event to:

Pharmacovigilance Office, OCTO Email: [contact] [contact]

If the SAE has not been reported within the specified timeframe, a reason for lateness must be provided when sending the SAE Report Form.

Investigators should also adhere to their local Trust/Board policy for incident and SAE reporting in research.

14.7 Follow-up of Serious Adverse Events

A follow-up report must be completed when the SAE resolves, is unlikely to change, or when additional information becomes available. If the SAE is a suspected SUSAR, then follow up information must be provided as requested by the Trial Office.

If new or amended information on a reported SAE becomes available, the Investigator should report this on a new SAE form using the completion guidelines.

SAEs that are considered to be probably or definitely unrelated to any trial intervention will not be followed up and monitored.

14.8 Reporting Adverse Events on the CRF

All AEs, including Serious AEs must be recorded on the eCRF for registered patients, unless otherwise specified in section 14.9. The information provided will include date of onset, event diagnosis (if known) or sign/symptom, severity, time course, duration and outcome and relationship of the AE to study drug. Any concomitant medications or any other therapy used to treat the event must be listed. The Investigator will provide an "other" cause for serious AEs considered to be unrelated to the study drug. Sites should ensure data entered into the eCRF is consistent with the SAE report information where applicable.

Each separate AE episode must be recorded. For example, if an AE resolves completely or resolves to baseline and then recurs or worsens again, this must be recorded as a separate AE. For AEs to be considered intermittent, the events must be of similar nature and severity.

AEs may be spontaneously reported by the patient and/or in response to an open question from study personnel or revealed by observation, physical examination, or other diagnostic procedures. Any clinically relevant deterioration in laboratory assessments or other clinical finding is considered an AE.

Terms and Grading of Events

All adverse events and toxicities must be graded according to the NCI Common Terminology Criteria for adverse events (NCI CTCAE) Version 4.0 (currently up to Version 4.03). Toxicity grades should be recorded on the eCRF. These will be coded by OCTO to the MedDRA version current on the date of MHRA approval of the trial.

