8 INVESTIGATIONAL MEDICINAL PRODUCT (IMP)

The trial is investigating the use of atovaquone suspension in combination with chemoradiotherapy. Atovaquone, cisplatin and vinorelbine are all considered Investigational Medicinal Products (IMPs) in this trial due to the investigation of these drugs being used in a novel combination.

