18.1 Inclusion in analysis

All patients enrolled in the study and who received at least one dose of atovaquone will be accounted for and included in the analyses. The number of patients who were not evaluable, who died or withdrew before treatment began will be recorded. The distribution of follow-up time will be described and the number of patients lost to follow-up will be given.

The analysis will include a description of patients who did not meet all the eligibility criteria, an assessment of protocol deviations, study drug accountability and other data that impact on the general conduct of the study. Baseline characteristics will be summarised for all enrolled patients. Patients who died or withdrew before treatment started or do not complete the required safety observations will be described and evaluated separately. Treatment-related toxicity will be tabulated by type and grade of toxicity. All patients will be evaluable for toxicity from the time of their first treatment. Adverse events will be summarised by the number of patients experiencing each type of event. The grades and causality will be reported.

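### The causality scale and the listed eCRF item grade relation to study drug, so an adverse event due to radiotherapy alone can be left out of the treatment-related toxicity table

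*Protocol*

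**What the plan says.** Protocol 14.3 opens broadly: related events include "any AE that is documented as possibly, probably or definitely related to protocol treatment". The scale beneath is narrower. Its two classes are drug-related and not drug-related, and each of the five grades is defined by reference to study drug. The lowest grade, for example, reads "The AE is definitely not associated with the study drug administered". The investigator is then told to "give their opinion of the causal relationship between each AE and study drug".

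Protocol 14.8 lists what goes on the eCRF for every AE. The causality element is the "relationship of the AE to study drug". A fallback exists only for serious events: the investigator supplies another "cause for serious AEs considered to be unrelated to the study drug".

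Section 8 states that "Atovaquone, cisplatin and vinorelbine are all considered Investigational Medicinal Products (IMPs) in this trial". Radiotherapy is not among them. The serious adverse reaction definition in 14.3 covers an IMP alone or together with radiotherapy, but not radiotherapy alone.

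On the analysis side, protocol 18.1, repeated in SAP 3.7, says "Treatment-related toxicity will be tabulated by type and grade of toxicity" and that causality will be reported. Neither place defines treatment-related.

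DLTs have a separate test in section 9.1, repeated in SAP Appendix 4. The event must be "assessed by the Principal Investigator as possibly, probably or definitely related to atovaquone and/or to chemoradiotherapy".

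**The concern.** The trial adds a drug to thoracic chemoradiotherapy, and the safety objective concerns the combination. Oesophagitis and pneumonitis, both named in section 9.1, are toxicities that an investigator may reasonably put down to the radiation. An investigator who does so and then follows the 14.3 scale as written has to grade the event as not drug related, although the opening of the same section would count it as related.

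If the treatment-related table is built from that item, such an event drops out of it. Two sites with identical patients could also differ, one following the opening sentence of 14.3 and the other following the scale. At stake is the descriptive safety profile that the trial reports as a secondary objective and that a later efficacy trial would draw on.

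**Working it through.** The plan states no figure on this point, so none can be reproduced. The check is a comparison of texts, followed by a calculation for scale only.

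**Step 1. What each place measures relatedness against.**

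| Place | Reference for relatedness | Radiotherapy alone covered? |
|---|---|---|
| Protocol 14.3, opening | protocol treatment | yes |
| Protocol 14.3, five-grade scale | study drug | no |
| Protocol 14.3, serious adverse reaction | an IMP, alone or with radiotherapy | no |
| Protocol 14.8, eCRF item | study drug | no |
| Protocol 14.8, other cause | free alternative, serious AEs only | yes, if serious |
| Protocol 14.7, SAE follow-up | any trial intervention | yes |
| Protocol 14.9, deaths | IMP or other protocol treatment | yes |
| Protocol 9.1 and SAP Appendix 4, DLTs | atovaquone and/or chemoradiotherapy | yes |
| Protocol 18.1 and SAP 3.7, toxicity table | treatment, undefined | unclear |

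I read study drug as all three IMPs, which is the reading kindest to the plan. The component left without a grade is then radiotherapy.

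**Step 2. Follow one event through.** Take an AE that the investigator ascribes to radiotherapy and to none of the three drugs.

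- On the 14.3 scale it falls in the not-drug-related class.
- On the listed eCRF item it is unrelated.
- If it is serious, radiotherapy can be entered as the other cause and recovered later.
- If it is not serious, nothing listed records radiotherapy as the cause.
- In the 18.1 table it is missing if treatment-related is derived from the listed item.

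**Step 3. Scale.** Inputs: n = 20 (protocol 17.4); grade 3 or higher oesophagitis 6% (12.5), about 25% on average and up to 48% (17.1); grade 3 or higher pneumonitis 4% (12.5) and up to 32% (17.1). Expected patients with the event = n × p:

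- Oesophagitis: 20 × 0.06 = 1.2; 20 × 0.25 = 5.0; 20 × 0.48 = 9.6.
- Pneumonitis: 20 × 0.04 = 0.8; 20 × 0.32 = 6.4.

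These are all such events expected under chemoradiotherapy. Let q be the share ascribed to radiotherapy alone. The expected number affected is n × p × q. The documents do not give q, so I let it run from 0 to 1, and the number affected runs from 0 up to each count above.

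Most of these grade 3 or higher events also travel on the SAE form, either as DLTs or as clinically significant grade 3 or higher events (14.11), so a cause can be entered for them. The clear gap is in non-serious, mostly lower-grade events. The documents give no usable rate for those: the rows for grade below 3 in section 12.5 sum with their counterparts to 94 + 6 = 100% and 97 + 4 = 101%, so they look like complements that include patients with no event. I do not use them.

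**The case against.** The strongest reply is that the protocol plainly intends radiotherapy to count. The opening of 14.3, the SAE follow-up rule in 14.7 and the death rule in 14.9 all use terms wider than study drug. This stands as far as it goes: the protocol as a whole is not confined to drug causality. It does not repair the scale or the listed item, and it shows that 14.3 disagrees with itself.

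Second, few events may be affected. A possibly related grade needs only suitable timing and a reasonable possibility. Atovaquone is given throughout chemoradiotherapy as a radiosensitiser, and cisplatin and vinorelbine are IMPs too. An event is misgraded only if the investigator rules out all three. This stands, and it is why the lower limit is 0.

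Third, the list in 14.8 need not be complete, and the eCRF, the SAE form and the table templates in SAP Appendix 3 are separate documents that may already hold separate fields. This also stands. The gap is in what the protocol and SAP specify; the forms themselves cannot be judged from here.

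A reader might go further and infer that radiotherapy-induced DLTs go uncounted and bias the DLT rate downwards. The documents do not support that. DLT relatedness has its own rule in section 9.1 and SAP Appendix 4, which names chemoradiotherapy. The clinician flags DLTs in the notes (5.3.2), they go on the SAE form within 24 hours (9.1), and a dedicated CRF serves dose decisions (SAP 6.3). Nothing derives DLT status from the eCRF causality item. Section 9.1 does borrow grade words that are defined only in the 14.3 scale, but a DLT would be lost only if a Principal Investigator set the explicit rule aside.

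Nor would radiotherapy toxicity vanish from the report. Protocol 18.1 and SAP 6.1 also present AEs without a relatedness filter.

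**Conclusion.** The point holds as an internal inconsistency with a limited consequence. Section 14.3 promises relatedness to protocol treatment, then supplies a scale, and 14.8 a data item, that grade relatedness to study drug. Followed literally, an AE due to radiotherapy alone is classed as not drug related, and if it is non-serious no listed item preserves the true cause. The treatment-related table and causality reporting can therefore understate radiotherapy toxicity.

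The size is unknown and may be nil. For the grade 3 or higher events used for scale, it lies between 0 and the counts shown, and most of those have another route for recording the cause. The all-AE summaries do not change. No effect on the MTD, the sample size or the operating characteristics of the TiTE-CRM is shown.

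The conclusion assumes that study drug means the three IMPs, that sites apply the scale as worded, that the tables use the item listed in 14.8, and that the unseen forms do not already collect radiotherapy attribution. It is worth correcting because the correction is cheap and attribution cannot readily be rebuilt afterwards for non-serious events.

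**What to change.** - Reword the 14.3 scale and the 14.8 item so that relatedness is recorded separately for atovaquone, for cisplatin/vinorelbine and for radiotherapy. Add durvalumab where it is given, since section 9.1 relies on that attribution as well.
- Align the SAE form and the eCRF if they do not already hold these fields.
- In protocol 18.1 and the SAP, define treatment-related as at least possibly related to any protocol treatment component, and use that definition in the table templates.
- Keep an IMP-only item for SUSAR assessment, where a drug-specific judgement is needed.

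A lesser change would replace study drug with protocol treatment in the scale and the item. That removes the contradiction but does not let the report separate the components.

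The cost is protocol and SAP wording and a few extra form fields, or wording alone if the forms already collect this. If AEs have already been entered without these fields, sites would need a one-off query to complete them. No design feature or analysis method changes.
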